Pediatric Pain Assessment in the Emergency Department

NCT03157882

October 13, 2017

Primary Investigator:

[name] Pediatric Emergency Medicine Fellow Department of Emergency Medicine Division of Pediatric Emergency Medicine [name]

Co-Investigators:

[name] Department of Emergency Medicine Division of Pediatric Emergency Medicine [name] [contact]

[name] Research Director Department of Emergency Medicine [name] [contact]

[name], CCRA Department of Emergency Medicine [name] [contact]

[name] [name], MSPH Director of Research in Biostatistics Dickson Advanced Analytics [name] [contact]

Purpose:

To examine how pediatric pain scales are used in clinical practice in a pediatric emergency department (ED). Specifically we will examine the use of Wong-Baker FACES ® Pain Rating Scale (WBF) and Faces Pain Scale – Revised (FPS-R) by ED nurses, as well as the correlation of results with the children's subjective descriptions of pain before and after an analgesic intervention as well as parental estimates of their children's pain. We will determine if a child's successful use of these scales can be predicted by evaluating his/her neurocognitive development.

Background:

"Most children five years and older can provide meaningful self-reports of pain if they are provided with age appropriate tools and training."¹ Self-report is the desired method of data collection.^{2,3} Face scales provide an ordinal self-report of pain, and the literature suggests that they are the preferred method of pain reporting by children.²

Both the WBF and the FPS-R have been studied extensively in children with chronic pain, postoperatively, and those experiencing procedural pain; however, data for their use in assessing acute pain while in the ED is limited. It is imperative that pain be assessed accurately, as it is the most common reason for presentation to the ED. However, it is also important because often we draw conclusions about the efficacy of an intervention based on the results of these pain scales.

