
Convergent validity will be assessed by determining both Pearson's correlation and agreement using the Bland-Altman method between the WBF and FPS-R scores before and after analgesic intervention. We will compare Pearson correlations using Fisher r-to-Z transformation.

Inter-rater reliability will be determined by calculating intra-class correlation coefficients (ICCs) between the parent and the child reports at the same time points.

This analysis will be completed with the biostatistics team under the direction of CORE (Center for Outcomes of Research and Excellence).

Subject #						
Observed Pain Assessment						
Start Time:	End Time:		RN:			
Initial pain scale used						
Wong Baker FACES	Numerical	Othe	er			
Initial phrasing of question						
How is the question framed?						
Zero		Ten				
No pain		Wors	st pain exp	erienc	ed	
No hurt		Worst pain p	oossible			
Other	_	Other				
Example given for 10/10?			Yes		No	
Patient's initial response						
Time to give answer						
Is the question rephrased?			Yes		No	
Final scale used						
Wong Baker FACES	Numerical	Othe	er			
Is parent asked for confirmation?			Yes		No	
Does the parent rate the child's pa	Yes	_/10	No			
Is parent asked for their perception?					No	
Other tasks completed during assessment?					No	
Vitals Mea	lication					
Is "happy because there is no pair	Yes		No			
Is "you do not have to be crying" r	Yes		No			
Final score documented						
Does the RN believe the child und	Yes		No			
Does the caregiver believe the ch	Yes		No			

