Appendix 2 – Neurocognitive Assessment (Phase 2 Primary Aims #1 and #2)

Part I: Neurocognitive Skills Assessment

Classification

Children will be asked to "put together things that are alike" to determine their ability to classify objects. First they will be presented with a total of nine squares of paper of equal size (three red, three blue, and three yellow) and will be expected to group them by color. They will then be presented with nine faces from the WBF (three of 0/10, three of 4/10, and three of 10/10) and asked to group similar faces. Finally, they will be presented with nine faces from the FPS-R (three of 0/10, three of 4/10, and three of 10/10) and asked to group similar faces. Finally, they each group properly similar faces. Final score will be 0-3 points, with one point assigned for each group properly classified.

Seriation

Participants will be asked to put a series of six squares with increasing size in order from smallest to largest. They will then be asked to put the six individual faces from WBF in order from least pain to most pain. They will repeat the task with the six individual faces from FPS-R. Final score will be 0-3, with one point assigned for each group properly ordered.

Magnitude of Pain

Using pictures and scenarios from the Charleston Pediatric Pain Pictures (CPPP),⁹ participants will be asked whether the pictures show "no hurt," "a little hurt," or "a lot of hurt" and will be assigned one point for each scenario properly classified for a total of 0-3 points.

Matching

Using pictures from the CPPP, participants will assign face scale levels of pain to a no-pain, a medium-pain, and a severe-pain picture using the WBF (0/10, 4/10, and 10/10) and the FPS-R (0/10, 4/10, and 10/10). They will receive one point for each scenario correctly matched for a total of 0-6 points.

Reverse Matching

Participants will be shown faces from the WBF and FPS-R (0/10, 4/10, and 10/10) and asked to select a pain scenario from the CPPP to match. They will receive one point for each scenario properly matched for a total of 0-6 points.

Part 2: BRIGANCE ® Early Childhood Screens III

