Appendix 4 – Caregiver Survey (Phase 2 Secondary Aim #2)

Part One

Thank you for agreeing to participate in this study of pain scales used in children. Your responses will help us make sure we are doing the best job we can to address your child's pain. Please do not ask your child about his/her pain while you answer these questions.

What do you believe is hurting on your child?

These faces show how much something can hurt. The face on the far-left shows no pain. The faces show more and more pain up to the far-right. It shows very much pain.

Please circle the face that shows how much you think your child hurts right now.

Each face below is for a person who has no pain, or some, or a lot of pain. Face 0 doesn't hurt at all. Face 2 hurts just a little bit. Face 4 hurts a little bit more. Face 6 hurts even more. Face 8 hurts a whole lot. Face 10 hurts as much as you can imagine, although you don't have to be crying to have this worst pain.

Please circle the face that represents your child's pain right now.

Part Two

Your child has received medications to help lessen his/her pain. Please answer the following questions about your child and his/her level of pain right now.

Please do not ask your child about his/her pain while you answer these questions.

These faces show how much something can hurt. The face on the far-left shows no pain. The faces show more and more pain up to the far-right. It shows very much pain.

Please circle the face that shows how much you think your child hurts right now.

Each face below is for a person who has no pain, or some, or a lot of pain. Face 0 doesn't hurt at all. Face 2 hurts just a little bit. Face 4 hurts a little bit more. Face 6 hurts even more. Face 8 hurts a whole lot. Face 10 hurts as much as you can imagine, although you don't have to be crying to have this worst pain.

Please circle the face that represents your child's pain right now.

Do you think your child is in less pain than when you last rated his/her pain in Part One? (Circle your answer)

Yes No

If yes, what makes you believe his/her pain is less`?

If no, what makes you think his/her pain is not less?

Part Three

If you do not feel that your child's pain has improved, please notify a provider at this time.

Please answer the following questions about your child's ability to report his/her pain.

Do you think that your child would understand the pain scales you used to rate his/her pain?

(Circle your answer)

Yes No

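### Bland-Altman is the only agreement measure planned for two six-face ordinal scales; conventional 1.96 SD limits need not hold 95% of children, so agreement should be reported in faces

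*Combined protocol and SAP*

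**What the plan says.** Phase 2 Secondary Aim #1 asks whether the WBF and FPS-R give similar results in children with acute pain. In Statistical Analysis, Phase 2, this is to be assessed by Pearson's correlation and "agreement using the Bland-Altman method between the WBF and FPS-R scores before and after analgesic intervention". The section gives no level for the limits, no difference that would count as acceptable, and no other agreement measure for this aim.

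On the scores themselves:
- Background: "Face scales provide an ordinal self-report of pain".
- Appendix 2, Seriation: children order the "six individual faces from WBF in order from least pain to most pain", then the "six individual faces from FPS-R". Each scale therefore has six levels.
- Appendix 4: one caregiver script, read here as the WBF, numbers its faces in twos: "Face 2 hurts just a little bit. Face 4 hurts a little bit more. Face 6 hurts even more".
- Appendix 2, Classification and Matching: FPS-R faces are labelled 0/10, 4/10 and 10/10. The full FPS-R numbering is not written out.

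**The concern.** Limits set at the mean ±1.96 SD contain about 95% of differences when those differences are roughly continuous and normal. Differences between two six-level scores in steps of 2 are neither: they sit on a few values, usually with a spike at 0. The limits land between attainable values, and the share of children inside jumps as a limit crosses a multiple of 2.

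The usual reading of such limits could then be wrong in either direction. Limits of about ±1.5 would suggest that 95% of children are within 1.5 points, when 15% may in fact differ by a full face. Pearson's correlation does not fill the gap. It is unchanged by a constant shift between the scales, so it cannot show whether children pick the same face. That leaves the Bland-Altman output as the only planned evidence on agreement.

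**Working it through.** The plan gives no figure for this analysis, so there is nothing to reproduce. The Phase 2 size of about 250 comes from the age strata (5 cognitive ages × 50 = 250), not from this aim.

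**Inputs.** Six faces per scale (Appendix 2) and a step of 2 points (Appendix 4; inferred for the FPS-R from six faces that include 0, 4 and 10). Assumptions: limits at mean ±1.96 SD, and the distribution of D = WBF − FPS-R, which the documents do not give and which is therefore varied.

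**1. One-face disagreement only, no bias.** A share p of children differ by ±2, equally in each direction. SD = 2√p, so the limits are ±1.96 × 2√p = ±3.92√p. These are below 2 when p < (1/1.96)² = 0.260.

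| p one face apart | limits | share inside |
|---|---|---|
| 2% | ±0.55 | 98% |
| 5% | ±0.88 | 95% |
| 10% | ±1.24 | 90% |
| 15% | ±1.52 | 85% |
| 20% | ±1.75 | 80% (50 of 250 outside) |
| 25% | ±1.96 | 75% |
| 30% | ±2.15 | 100% |

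**2. Floor.** By Chebyshev's inequality, at least 1 − 1/1.96² = 74.0% of any distribution lies within 1.96 SD of its mean. The range of about 74% to 100% is therefore general and not special to step 1.

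**3. All disagreement in one direction.** Mean = 2p and SD = 2√(p(1−p)). The upper limit is below 2 when p < 1/(1 + 1.96²) = 0.2065. Just below that point coverage is about 79%.

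**4. Mixed disagreement, no bias.** Variance = 4p₁ + 16p₂ + 36p₃ for shares one, two and three faces apart.
- 15%, 2%, 0%: variance 0.92, limits ±1.88, coverage 83%.
- 30%, 5%, 0%: variance 2.00, limits ±2.77, coverage 95%.
- 35%, 3%, 0%: variance 1.88, limits ±2.69, coverage 97%.
- 30%, 8%, 2%: variance 1.20 + 1.28 + 0.72 = 3.20, SD 1.79, limits ±3.51, coverage 90%.

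**5. Latent normal scores rounded to six faces** (assumed mean 6, SD 3, no bias). Coverage does not move steadily with agreement: 95.0% at observed r = 0.56, 97.4% at 0.66, 89.2% at 0.76, 93.0% at 0.81, 96.8% at 0.86, 99.5% at 0.91 and 78.6% at 0.94.

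**6. When one-face differences drop out.** With no bias this needs SD(D) < 2/1.96 = 1.02. With equal score SDs s, SD(D)² = 2s²(1−r), so r must exceed 1 − 1.041/(2s²). That is 0.917 for s = 2.5 and 0.942 for s = 3.

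**7. In a sample of 250.** Under the model of step 1, the simulated chance that the sample limits exclude both +2 and −2 is 96% at p = 20%, 60% at 24%, 32% at 26% and 4% at 30%.

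**8. Precision of the alternative.** For a proportion with n = 250, the 95% half-width is at most 1.96√(0.25/250) = 6.2 points by the normal approximation. The exact interval is slightly wider.

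**The case against.** The plan names a method in a single sentence. It does not write 95%, 1.96 SD or any claim of 95% agreement, and it does not rule out empirical limits or a cross-tabulation. This stands: everything above about limits is conditional on the conventional default.

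A reader might infer that the limits generally fail to hold 95% of children. The working does not support that, since coverage is 95% or more in many patterns and 100% when more than 26% of children differ by exactly one face without bias.

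A reader might also infer that every one-face disagreement would be hidden. That needs very close agreement, and the protocol itself doubts that the youngest children use these scales reliably. Close agreement is, however, the direction of the stated hypothesis for this aim, so the case cannot be set aside.

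The strongest objection is that no conclusion is shown to change. In the one-face-only example every child is within one face, so narrow limits and the within-one-face rate would both point to convergence. This also stands. The defect lies in the stated degree of agreement, not in a demonstrated wrong verdict.

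Finally, the six-level scores are recorded on the surveys, so nothing is lost for good. That makes the remedy cheap, but it does not supply an agreement measure that the plan now lacks.

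**Conclusion.** The point holds in a limited form. With scores in steps of 2, conventional Bland-Altman limits have no dependable 95% coverage. The share inside lies between about 74% and 100%, and the limits omit all one-face differences when fewer than about 26% of children are one face apart without bias (about 21% if all disagreement runs one way). The plan offers no acceptable difference and no ordinal agreement measure to fall back on.

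This rests on three assumptions: that the default 1.96 SD limits are meant, that the FPS-R is scored in twos, and that the illustrative distributions are plausible. The documents do not support saying that the plan commits to 95% limits, that such limits are wrong in general, or that the convergent-validity conclusion would be reversed. It is a cheap improvement to a secondary aim, with no effect on the sample size or the primary aims.

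**What to change.** In Statistical Analysis, Phase 2, for each time point:
- Keep the mean WBF − FPS-R difference with its CI, and the Bland-Altman plot. State that the 1.96 SD limits, if drawn, are not to be read as containing 95% of children.
- Report the 6x6 cross-tabulation and the observed percentages identical, within one face, and two or more faces apart in each direction, with exact 95% CIs (half-width at most about 6 points at n = 250).
- Optionally add a weighted kappa, noting that quadratic weights treat the faces as equally spaced, or the empirical 2.5th and 97.5th percentiles of the difference.
- Base the agreement statement on these percentages.
- Write out the score values of both scales, so that the 2-point step is explicit.

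The cost is a few lines of plan text and one table per time point, from data already collected. The small downside is that the result is less directly comparable with studies that report conventional limits of agreement.

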Appendix 1 – Qualitative Assessment (Phase 1 Primary Aim)

Investigator Initials: _____ Date: _____

Appendix 2 – Neurocognitive Assessment (Phase 2 Primary Aims #1 and #2)

Part I: Neurocognitive Skills Assessment

Classification

Children will be asked to "put together things that are alike" to determine their ability to classify objects. First they will be presented with a total of nine squares of paper of equal size (three red, three blue, and three yellow) and will be expected to group them by color. They will then be presented with nine faces from the WBF (three of 0/10, three of 4/10, and three of 10/10) and asked to group similar faces. Finally, they will be presented with nine faces from the FPS-R (three of 0/10, three of 4/10, and three of 10/10) and asked to group similar faces. Finally, they each group properly similar faces. Final score will be 0-3 points, with one point assigned for each group properly classified.

Seriation

Participants will be asked to put a series of six squares with increasing size in order from smallest to largest. They will then be asked to put the six individual faces from WBF in order from least pain to most pain. They will repeat the task with the six individual faces from FPS-R. Final score will be 0-3, with one point assigned for each group properly ordered.

Magnitude of Pain

Using pictures and scenarios from the Charleston Pediatric Pain Pictures (CPPP),⁹ participants will be asked whether the pictures show "no hurt," "a little hurt," or "a lot of hurt" and will be assigned one point for each scenario properly classified for a total of 0-3 points.

Matching

Using pictures from the CPPP, participants will assign face scale levels of pain to a no-pain, a medium-pain, and a severe-pain picture using the WBF (0/10, 4/10, and 10/10) and the FPS-R (0/10, 4/10, and 10/10). They will receive one point for each scenario correctly matched for a total of 0-6 points.

Reverse Matching

Participants will be shown faces from the WBF and FPS-R (0/10, 4/10, and 10/10) and asked to select a pain scenario from the CPPP to match. They will receive one point for each scenario properly matched for a total of 0-6 points.

Part 2: BRIGANCE ® Early Childhood Screens III

Appendix 3 – Patient Survey (Phase 2 Primary and Secondary Aims)

Part One

Time: _____

1. Does anything hurt on you right now?

2. Faces Pain Scale-Revised reported score:

3. Wong-Baker FACES ® reported score:

Medication:

Time administered: _____

Part Two

Time:									
1. Do you feel	better, wors	e, or the same	?						
Better (go to Se	ection A)	Worse (go to Section B)		Same (go to Section C)					
Section	пA								
	Do you feel	a little bit bette	r or a lot bett	er?					
	A little	e bit	A lot						
	Does anything hurt on you right now?								
	Yes	0 ,	No						
,	What hurts on you right now?								
Section	n B								
Do you feel a little bit worse or a lot worse?									
	A little	e bit	A lot						
	What hurts on you right now?								
	🗆 MD notifie	ed							
Sectior	n C								
I	Does anything hurt on you right now?								
	Yes		No						
	What hurts on you right now?								
	🗆 MD notifie	ed							
2 Eason Dain	Saala Bavia	ad reported as							

2. Faces Pain Scale-Revised reported score:

3. Wong-Baker FACES ® reported score:

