Hypothesis: Children with a cognitive age equivalent of at least five years old will more reliably use the WBF and FPS-R to self-report acute pain when presenting to the emergency department

Rationale: Multiple studies have compared children's ability to use pain scales based on age, and both the WBF and FPS-R are conventionally believed to be appropriate for children once they are four years old. However, age is used as a proxy for developmental level; not all four year old children have the developmental and cognitive skills to quantify and report their pain. Whether children have the skill set to complete a self-report of pain is variable until approximately the age of five years. This study would serve to more clearly classify the level of cognitive development needed to use the pain scales effectively.

Methods Summary: Prospective, observational study to determine if there is correlation between neurocognitive development and responsivity when using the WBF and FPS-R as well as the minimum cognitive age equivalent needed to effectively use the WBF and FPS-R. Initial and repeat WBF and FPS-R self-report scores will be compared at two points during the ED evaluation of patients presenting with acute pain. The change in the WBF and FPS-R pain scores will be compared to the subjective self-reports of change in pain. Children will complete the BRIGANCE ® Early Childhood Screens III to determine whether they are at, above, or below the expected cognitive development for their age. Children with at or above expected cognitive development. Children will also complete a series of tasks aimed to assess ability to successfully use the WBF and FPS-R (Appendix 2). Children that complete all tasks successfully will be compared to those who do not. The BRIGANCE will also be used to determine the cognitive age equivalent for each subject. We will determine the minimum cognitive age equivalent for each subject. We will determine the minimum cognitive age equivalent for each subject. We will determine the minimum cognitive age equivalent associated with accurate use of the WBF and FPS-R, defined as a self-report that matches the subjective report of change in pain.

Phase 2 – Secondary Aim #1:

To determine whether the WBF and FPS-R exhibit convergent validity (degree to which they produce similar results) when used with children presenting to the emergency department with acute pain

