Exclusion criteria

Altered mental status History of traumatic brain injury (TBI) History of developmental delay History of Autism History of chronic pain, defined as persistent or recurrent pain in children with chronic health conditions⁸ Non-verbal patients

Outcome Measures:

Phase 1 - Primary Aim

Rate of intended script use in pain scale delivery Review of themes during nursing pain assessment Consistency in delivery of WBF by nursing

Phase 2 - Primary

Neurocognitive development score BRIGANCE ® score Initial WBF score Repeat WBF score Initial FPS-R score Repeat FPS-R score Anchor report of pain (a lot better, a little better, the same, a little worse, a lot worse)

Phase 2 - Secondary

Initial WBF score (patient and caregiver) Repeat WBF score (patient and caregiver) Initial FPS-R score (patient and caregiver) Repeat FPS-R score (patient and caregiver)

Study Definitions:

"Caregiver" will refer to an adult who is able to provide consent for treatment and provides regular care for the child.

"Chronic pain" includes persistent (ongoing) and recurrent (episodic) pain in children with chronic health conditions.

Convergent validity evaluates the degree to which two different scales that are supposed to measure the same thing produce similar results.

"Repeat pain score" will be completed approximately 20 minutes after the initial pain score, or if administered, approximately 20 minutes after analgesic intervention.

Responsivity is the degree to which a test behaves in a manner that is consistent with what the test is purported to measure. It determines whether the measure is able to identify changes in pain over time that are clinically important to patients.

Phase 1 Study Protocol:

- 1. Once the subject is identified, the caregiver will provide verbal consent for participation in the study.
- 2. After verbal consent is obtained, the primary investigator will observe and audio record nursing's assessment of the patient's pain and complete the observation checklist (Appendix 1).

Phase 2 Study Protocol:

- 1. Once the subject is identified, the caregiver will provide written consent for participation in the study (if a self-report pain score was not collected in the triage process, patients with pain or a potentially painful condition will have their pain assessed using an age appropriate self-report pain scale by the PI or designee).

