Responsivity will be measured by correlating the change in the WBF and FPS-R scores before and after analgesic intervention with the anchor change in pain score (a lot better, a little better, the same, a little worse, a lot worse). Pearson correlations will be estimated between each change score and the anchor score. In addition, we will use ANOVA to test the difference in mean pain change among the children reporting "a lot better", "a little better", and "the same". For the scales to be considered responsive, we would need to see significant reductions for the children reporting "a lot better", minimal to no reduction for those reporting "the same", and increase in pain for those reporting "worse". We will need a relatively large number of children in each category (a lot better, a little better, the same) to be able to test for differences (at least 30 per group). We will use Fisher's z-transformation to test if level of neurocognitive development impacts responsivity. Levels of neurocognitive development will be defined as at or above expected or lower than expected. The Fisher's z-transformation formally tests if the correlations between two measures (change in pain and anchor rating) differ between two groups. Here we assume we will have significant variability in change scores and in the anchor ratings to conduct these correlations and the formal test. We would need at least 56 children in each neurogcognitive development group (expected or above versus below). If the variability is limited in that most children report improvement and few report same or worsening, we will test for responsivity differences using a two-way ANOVA where the two factors are self reported anchor response ("better", "same" or "worse) and neurocognitive level (expected or above expected vs below expected). The outcomes are the change in the WBF and the change in the FPS-R. The test of interest will be the two way interaction between the anchor and the neurocognitive development level. The BRIGANCE also provides the developmental age for each child which can be compared to their actual age. We will test if this difference is significant using a paired t-test. We will also explore the age where responsivity worsens by conducting similar analyses but stratified by actual age (each year) and developmental age. Given the proposed analysis, we will need at least 50 children for each cognitive age (3, 4, 5, 6, and 7 years) assuming at least 10 fall into the "a lot better", "a little better", "the same" categories for the anchor pain question.

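### The child's anchor question names neither hurt nor a comparison time, although both Phase 2 primary aims judge the scales against it

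*Combined protocol and SAP*

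**What the plan says.** Outcome Measures (Phase 2 - Primary) lists the anchor as "Anchor report of pain (a lot better, a little better, the same, a little worse, a lot worse", that is, as a five-level report about pain. It has two uses:

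- **Aim #1.** The Phase 2 part of Statistical Analysis measures responsivity by "correlating the change in the WBF and FPS-R scores before and after analgesic intervention with the anchor change in pain score", and adds that "Pearson correlations will be estimated between each change score and the anchor score". These correlations are then compared between children at or above and children below expected development.
- **Aim #2.** The methods summary for the Phase 2 primary aims calls scale use accurate when it is "defined as a self-report that matches the subjective report of change in pain".

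The item that supplies the anchor is Appendix 3, Part Two, item 1. The child chooses between better, worse and the same, and a follow-up asks for the degree, for example "Do you feel a little bit worse or a lot worse". Questions on hurt come only after that answer and concern the present: "Does anything hurt on you right now".

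The caregiver's question on change (Appendix 4, Part Two) is more explicit: "Do you think your child is in less pain than when you last rated his/her pain in Part One".

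On timing, Study Definitions says that the repeat score "will be completed approximately 20 minutes after the initial pain score, or if administered, approximately 20 minutes after analgesic intervention". Step 5 of the Phase 2 Study Protocol also times Part Two from the analgesic. Part One is placed only early in the visit (step 2).

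**The concern.** The change score has a fixed meaning: pain at Part Two minus pain at Part One. The anchor is the criterion against which that change is judged, so it should cover the same feeling over the same interval. As printed, it specifies neither. A child may answer about feeling unwell in general, or may compare with arrival, with the injury, or with the moment before the medicine.

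Two consequences follow. Misdirected answers lower the change-anchor correlation of a scale that works, and under Aim #2 a child who used the faces correctly can be counted as inaccurate. Further, enrolment runs from 3 years to 7 years six months, and the protocol's own rationale treats the self-report skill set as variable until about five. If children at a lower cognitive level are also less able to supply an unstated comparison, poor understanding of the anchor would look like poor use of the scales. That is the direction of both primary hypotheses.

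**Working it through.** **1. The two forms side by side.**

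| | Child (Appendix 3, Part Two, item 1) | Caregiver (Appendix 4, Part Two) |
|---|---|---|
| Feeling named | none | pain |
| Comparison time named | none | Part One |
| Use | criterion for Aims #1 and #2 | no analysis stated |

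The later hurt questions on the child's form cannot settle what the anchor meant. They follow it and ask about the present, not about change. No spoken script for the anchor is given.

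**2. The interval.** Under Study Definitions and step 5:

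- untreated child: Part One to Part Two is about 20 minutes;
- treated child: (delay from Part One to analgesic) + about 20 minutes.

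The documents set no limit on the delay. Assumed delays of 0, 30 and 60 minutes give intervals of 20, 50 and 80 minutes. A treated child therefore has at least two natural starting points, the first faces rating and the medicine, and the question does not choose between them.

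**3. Effect on the correlation (illustration; every input is assumed).** Let r be the change-anchor correlation when the anchor is read as intended, p the share of misdirected answers, and c the correlation of those answers with the change. With the same marginal distributions in both parts of the mixture,

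observed r = (1 − p) × r + p × c.

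With r = 0.60 in both groups, so that the scales perform equally well:

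| | p = 0.10 | p = 0.40 | Spurious difference |
|---|---|---|---|
| c = 0.40 | 0.54 + 0.04 = 0.58 | 0.36 + 0.16 = 0.52 | 0.06 |
| c = 0 | 0.54 + 0 = 0.54 | 0.36 + 0 = 0.36 | 0.18 |

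**4. What this would mean for the Fisher z test.** The plan asks for at least 56 children per development group but gives no alpha, power or correlations, so the figure cannot be reproduced from its own inputs. It is plausible: r = 0.5 versus 0.8, two-sided 5% and 80% power give 2 × ((1.960 + 0.842)/0.5493)² + 3 = 55.02, rounded up to 56.

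At 56 per group the standard error of the difference in z is √(2/53) = 0.194. Suppose that the 10% and 40% shares applied to the two development groups:

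- c = 0: z difference 0.6042 − 0.3769 = 0.227; ratio 0.227/0.194 = 1.17; chance of a significant result about 22%.
- c = 0.40: z difference 0.6625 − 0.5763 = 0.086; ratio 0.086/0.194 = 0.44; chance about 7%.

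The nominal rate is 5%. The result therefore runs from close to nominal to about four times nominal, depending on inputs that the documents do not supply.

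**The case against.** The strongest reply is context. Phase 2 children enter with a pain score of at least 4/10, Part One opens by asking whether anything hurts and uses two faces scales, and study staff help the child through both parts. A pain reading is then the natural one for many children, and staff may supply the frame aloud. This stands in part: it makes a wholly unrelated answer less likely. It does not fix the reference moment, and a frame supplied without a script may differ from child to child, which is the kind of variation that Phase 1 sets out to study.

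Three stronger readings are tempting, and the documents do not support them.

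- *The varying interval is itself an error.* It is not. The anchor and the repeat scores are taken in the same Part Two, so an anchor that pointed to Part One would cover the same interval as the change score, whatever its length. The times of Part One, medication and Part Two are recorded.
- *The bias in r is 0.18.* That figure needs misdirected answers to carry no information about the change. A child who compares with the moment before the medicine may well give an answer close to the intended one, which is why the smaller figure is shown beside it.
- *The study will wrongly find poorer scale use in less developed children.* This is a protocol with a hypothesis, not a result, and nothing in it shows that misdirected answers are commoner at low cognitive level. A contrast of younger with older children bears on Aim #2 and the exploratory age strata. Aim #1 compares children below with those at or above the level expected for their age, which is a different contrast.

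It is also fair to say that a question asking a three-year-old to recall an earlier rating is untested here and could itself fail more often at low cognitive age.

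**Conclusion.** The point holds as a defect in the wording of the criterion for both Phase 2 primary aims. That the item names neither hurt nor a comparison time is plain from the form, and nothing elsewhere in the documents supplies them. The consequence is conditional: misdirected answers weaken the correlation and the accuracy classification, and they favour the hypotheses only if they are commoner at low cognitive level. The size is unknown. The range of 0.06 to 0.18 in r rests on an assumed true correlation of 0.60, assumed shares of 10% and 40%, and an assumed 0.40 or zero correlation for misdirected answers. It shows direction and possible scale and is not an estimate. The varying interval is background: it explains why the reference moment is open for treated children. The change should be made because it is nearly free and brings the criterion into line with the change score.

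**What to change.** 1. Reword Appendix 3, Part Two, item 1 and its follow-ups in short, child-level language that names hurt and points to the first faces rating, for example: *Remember when I first showed you the faces? Is your hurt better, worse, or the same now?*, then *a little bit or a lot?* Showing the faces again would help to mark the moment.
2. Print the wording as a script and have every investigator or designee say it the same way.
3. If enrolment has begun, add a form version indicator so that the two wordings can be told apart in the analysis.
4. Report the Part One to Part Two interval from the recorded times, separately for treated and untreated children, as description only. I would not add a responsivity correlation restricted to short intervals: such a subset would over-represent untreated children, who may show less change, so a different correlation could reflect restricted range and not the anchor.

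The cost is one reworded item, a script line and a descriptive table from times already collected. The downside is a slightly longer question that asks the child to recall the first rating.
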